
	
 
• Question 2: Does reducing IPMS with a papillary muscle approximation stitch reduce the FMR severity after UMA, by improving valve geometry and biomechanics. We will conduct a pilot study of 15 patients with this approach and investigate their outcomes at 1 year after the surgery.
 

Hypothesis	Elevated IPMS is a risk factor for failure of UMA and recurrence of FMR at 12 months the repair. Reducing IPMS with a papillary muscle approximation stitch can reduce FMR recurrence after UMA.
Objectives	
 
(1) Determine if pre-surgery diastolic IPMS, systolic IPMS and (diastolic-systolic) IPMS correlates with the severity of FMR at immediate post-op, 30 days, 6 months, and 12 months post-UMA.
 
(2) Does IPMS reduction with PMA performed concomitantly with UMA, help in reducing the severity of FMR at immediate post-op, 30 days, 6 months, and 12 months after surgery.
 

Primary Endpoints	The primary endpoint of this study is to investigate if pre-operative inter-papillary muscle separation (diastolic, systolic and diastolic-systolic) correlates with FMR severity at 12 months after surgery with UMA and UMA+PMA.
Secondary Endpoints	
Survival
 
 
• All-cause mortality at discharge, 6 months and 1 year
 
 
Functional Status and Hospitalizations
 
 
• MACE (death, stroke, worsening heart failure (+1 NYHA Class), CHF hospitalization, mitral valve re-intervention at 6 months and 1 year
 
• NYHA classification at 6 months and 1 year
 
• 6-minute walk test at 6 months and 1 year
 
• Readmission rates at 6 months and 1 year
 
 
Physiologic
 
Pre-operative:
 
 
• MRI 
 
- MR severity
 
- Interpapillary muscle dynamics
 
- Left ventricular function
 
- Left ventricular geometry
 
- Left ventricular perfusion and motion defects
 
- Left ventricular scar burden
 
 
 
• Echo (transthoracic and transesophageal) 
 
- MR severity (ERO and regurgitant fraction)
 
 
 

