	
Rationale: The decision to perform mitral valve surgery could be made during the surgery by the surgeon, and these patients would be suitable for this study, but would not be consented prior to their surgery. Thus, in this registry, we will identify such patients for recruitment into this study, as their first research point isn't until 6 months after their surgery.
 
Step 1) Charts will be screened for patients who underwent surgery for the lesion of interest at Emory, who would otherwise be eligible for this study but were not recruited as it was not known if they will need mitral valve surgery.
 
Step 2) Patients who are still within 6 months (<math>\pm</math> 1 month) after the date of their surgery will be contacted after surgery and the study objective will be explained, verbal consent will be obtained and the date to visit Emory will be provided.
 
Step 3) Written consent will be obtained at their 6 month visit, and steps 9 and 10 described in registry # 1 will be performed.
 
Registry # 3: Retrospectively identified patients, who already underwent the standard of care surgery, and were identified after the procedure is completed, and are suitable for recruitment to the study for their post-operative research.
 
Rationale: Historical review of patients between dates 1/1/2004 to present who have undergone mitral valve surgery who were not previously identified in the study. These patients have not been consented prior to their surgery. The purpose is to increase the study sample size in order to gain statistical power for outcome analysis.
 
Step 1) Charts will be screened for patients who underwent surgery between 1/1/2004 to present for the lesion of interest at Emory, who would otherwise be eligible for this study but were not recruited as it was not known if they will need mitral valve surgery or were not recruited as they may have received the surgery prior to study start date.

Sample size	
140 subjects in total at Emory University.
 
Group 1: 125 patients to receive UMA and followed to 12 months, with interim imaging.
 
Group 2: 15 patients to receive UMA with PMA and followed to 12 months, with interim imaging.

	
It is expected that we will recruit ~25 patients per year.
 
Group 3: patients' medical charts will be queried between 2004 – present, number of subject charts are undetermined/unknown.

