## 2.0 OBJECTIVE

The primary objective of this protocol is to investigate if pre-operative inter-papillary muscle separation (IPMS) is predictive of FMR severity at 12 months after undersizing mitral annuloplasty (UMA) to repair functional mitral regurgitation (FMR). Furthermore, whether a cut-off value of pre-operative inter-papillary muscle separation can be established to predict patients who might have failure of UMA.

The secondary objective of this protocol is to investigate if adding papillary muscle approximation (PMA) to UMA is an effective technique in reducing recurrence of FMR at 12 months' post-procedure.

The third objective is to use computational modeling to define the impact that IPMS has on chordal force imbalance, to define the mechanistic basis for repair failure. MRI and echo images from the patients will be used to accomplish this objective.

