### **3.0 BACKGROUND**

Functional mitral regurgitation (FMR) is a frequently diagnosed mitral valve lesion in patients surviving cardiomyopathies of ischemic and non-ischemic origins. Volume overload from FMR increases the risk of congestive heart failure and death. Pharmacological management of these patients has been shown to be ineffective, and thus timely repair of FMR is considered to benefit the patient and preserve their cardiac function.

Undersizing mitral annuloplasty (UMA) is the current standard of care to repair FMR, which involves placing a metallic ring onto the mitral annulus, to reduce its dimensions. This procedure can be performed using open heart surgical techniques or with transcatheter mitral valve techniques. Though UMA is considered effective, there is increasing evidence that FMR persists or recurs after the procedure. At 12 months, ~36% of the patients present with recurrence FMR, which increases to 58% at 24 months. The mechanisms driving failure of UMA are unknown, and a metric for pre-operative stratification of patients to benefit from UMA is necessary.

Our group recently reported that in patients presenting with FMR, inter-papillary muscle separation (IPMS) has a strong correlation with the pre-operative severity of the regurgitation. Using cardiac MRI imaging, we demonstrated that IPMS directly impacted the extent of leaflet tethering and mitral regurgitation, independent of the left ventricular size or volume. We used biomechanical modeling to demonstrate that elevated IPMS increases the forces in the marginal chordae, resulting in improper leaflet closure.

In a more recent study in a bench-top ex-vivo model, we demonstrated that IPMS can also have an impact on mitral valve closure after undersizing mitral annuloplasty (UMA). Specifically, we demonstrate that when the IPMS is elevated, UMA results in a highly unphysiological leaflet geometry that results in persistent FMR despite the repair. In a similar study in swine, we demonstrated that such an unphysiological leaflet configuration after UMA can be improved with papillary muscle approximation (PMA).

In this observational, prospective, non-randomized clinical study, we seek to test the hypothesis that elevated pre-operative inter-papillary muscle separation (IPMS) is a risk factor for recurrence

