## 11.0 ANALYSIS PLAN

**General design issues:** This is an observational, prospective, non-randomized, single center, multiple phase study. Enrolled patients will have clinically significant FMR with either ischemic or non-ischemic cardiomyopathies. 50 patients are recruited to phase 1 (all 50 receiving undersizing mitral annuloplasty), and 90 patients to phase 2 (75 receiving undersizing mitral annuloplasty and 15 receiving undersizing mitral annuloplasty and papillary muscle approximation). In patients

receiving undersizing mitral annuloplasty, the same rigid annuloplasty ring will be used as consistently as possible, and up to two sizes of downsizing will be performed as consistently as possible. In some patients recruited to the study, the surgeon may decide to switch to mitral valve replacement, or may perform a repair and deem it to be a failure and then switch to mitral valve replacement. In either case, the patient will continue to be part of the study, but with follow-up performed only at 12 months.

**Sample size estimation and statistical analysis plan:** The primary objective of this study is to determine the correlation between pre-operative inter-papillary muscle separation and the 6 month and 12 month post-operative FMR grade after undersizing mitral annuloplasty. Pre-operative inter-papillary muscle separation will be measured and is a continuous variable, while the recurrence of FMR will be deemed binary (1: if MR greater than or equal to 2+ severity observed at 12 months; 0: if MR less than or equal to 2+ severity observed at 12 months). An ROC curve analysis will be used to determine the inflection point of inter-papillary muscle separation at which FMR will recur at 12 months after annuloplasty. Sample sizes are based on previously published data, and on ensuring the ability to detect with high probability, a clinically meaningful presumed benefit for patients undergoing mitral valve repair.

Recruitment to the papillary muscle approximation arm is not based on power analysis as it is only a pilot study.

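### Section 11.0 picks the IPMS cut-off by ROC in the study patients, with no optimism correction, interval for the cut-off or validation set, so accuracy reported at it would on average be optimistic

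*Combined protocol and SAP*

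**What the plan says.** Section 2.0 asks whether pre-operative IPMS predicts FMR severity 12 months after undersizing annuloplasty (UMA), and whether "a cut-off value of pre-operative inter-papillary muscle separation can be established to predict patients who might have failure of UMA". Section 11.0 gives the method: "An ROC curve analysis will be used to determine the inflection point of inter-papillary muscle separation at which FMR will recur at 12 months". It does not define the inflection point or mention an interval, covariates, resampling or a validation sample.

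The outcome for that ROC is coded "1: if MR greater than or equal to 2+ severity observed at 12 months; 0: if MR less than or equal to 2"+, so both classes include grade 2+.

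Other places that bear on the point:

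- **Phases (11.0).** "50 patients are recruited to phase 1 (all 50 receiving undersizing mitral annuloplasty), and 90 patients to phase 2"; phase 2 has 75 UMA patients and 15 who also receive papillary muscle approximation (PMA). Neither phase is named as derivation or validation.
- **Validation (3.0).** The cut-off is to be validated by computational force modelling on images from the same 125 patients. The 15 PMA pilot patients are to be those above the cut-off.
- **Registry 3 (1.0 and 7.2).** "The purpose is to increase the study sample size in order to gain statistical power for outcome analysis". Whether these patients enter the ROC is not stated.
- **IPMS measures (9.0).** Diastolic, systolic and difference values, each at tips, mid-body and base. None is primary.
- **Hypothesis (1.0).** "Elevated IPMS is a risk factor for failure of UMA and recurrence of FMR at 12 months", and "Reducing IPMS with a papillary muscle approximation stitch can reduce FMR recurrence after UMA".

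**The concern.** A cut-off chosen to fit one sample is partly fitted to that sample's noise. If its sensitivity and specificity are then read off the same sample, they overstate on average what new patients would show. The location of the cut-off is also imprecise, and without an interval a reader cannot see how imprecise.

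This matters inside the study as well as in the report, because section 3.0 uses the cut-off to choose the PMA pilot patients. The force modelling does not fill the gap. It asks whether patients on either side of the cut-off differ in valve forces, in the same people, and does not test again whether the cut-off predicts recurrence.

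The outcome coding is a separate defect that comes first: a patient with MR of exactly 2+ is both a recurrence and a non-recurrence, so the ROC outcome is undefined for that patient.

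**Working it through.** **The plan's own figure.** The 125 cannot be reproduced, because no alpha, power, AUC, correlation or dropout is given. A correlation of 0.25 with 80% power and two-sided 0.05 needs 124, but the documents state none of these, so the match may be chance. Nothing below depends on it.

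**Inputs from the documents.** 125 UMA patients, split 50 and 75 (11.0); 12-month recurrence 32.6% (1.0) or about 36% (3.0). Expected events: 125 × 0.326 = 41, or 125 × 0.36 = 45; phase 1, 50 × 0.326 = 16; phase 2, 75 × 0.326 = 24.

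**Assumptions not in the documents.** IPMS normal with equal variance in both outcome groups; true AUC 0.65, 0.70 or 0.75; cut-off maximising Youden's J = sensitivity + specificity − 1; one pre-specified IPMS measure; every patient evaluable. The sizes 300 and 500 illustrate what Registry 3 might add.

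**Formulas.** The separation in SD units is d = √2 × Φ⁻¹(AUC). At AUC 0.70, d = 1.414 × 0.524 = 0.742. The best attainable J, at the midpoint d/2, is 2Φ(d/2) − 1 = 2Φ(0.371) − 1 = 0.289. For a chosen cut-off c, true J = Φ(c) − Φ(c − d). Apparent J is the sample maximum. Optimism is the mean of apparent minus true.

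**Apparent / true J, 4,000 simulations per cell at 32.6% recurrence:**

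| n | AUC 0.65 | AUC 0.70 | AUC 0.75 | Optimism |
|---|---|---|---|---|
| 50 | 0.346 / 0.187 | 0.408 / 0.259 | 0.476 / 0.335 | 0.14–0.16 |
| 125 | 0.292 / 0.196 | 0.357 / 0.270 | 0.430 / 0.347 | 0.08–0.10 |
| 300 | 0.259 / 0.202 | 0.331 / 0.277 | 0.405 / 0.355 | 0.05–0.06 |
| 500 | 0.248 / 0.205 | 0.320 / 0.280 | 0.395 / 0.358 | 0.04 |

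At n = 125 and AUC 0.70, sensitivity is 0.69 apparent against 0.63 true, and specificity 0.67 against 0.64. The apparent J of 0.357 exceeds even the best attainable 0.289.

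**Instability.** In that same setting, the central 95% of chosen cut-offs leave between 19% and 72% of patients above the line.

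**AUC.** With one pre-specified measure the mean apparent AUC is 0.70 when the truth is 0.70, so it is not inflated. If the best of several measures were picked (assumed correlation between measures 0.9 to 0.5), it would be 0.71–0.73 for three and 0.73–0.75 for nine.

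**Does the remedy work?** Bootstrap correction at n = 125 gives apparent / corrected / true J of 0.298 / 0.232 / 0.197, 0.360 / 0.297 / 0.270 and 0.437 / 0.378 / 0.348 at the three AUCs. The share of optimism removed at AUC 0.70 is (0.360 − 0.297)/(0.360 − 0.270) = 0.70. At the other two it is 0.65 and 0.66, so about two-thirds overall.

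**Split-sample alternative.** Deriving in 50 and testing in 75 is unbiased. With about 24.4 events, though, the 95% half-width for a sensitivity near 0.6 is 1.96 × √(0.6 × 0.4/24.4) = 0.19.

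**The case against.** **The optimism is modest.** At n = 125 and AUC 0.70 it is 6 points of sensitivity and 3 of specificity. Sampling error is larger: 1.96 × √(0.63 × 0.37/41) = 0.15 and 1.96 × √(0.64 × 0.36/84) = 0.10. Registry 3 could shrink the optimism further. This stands as to size, but bias adds to sampling error, the plan provides an interval for neither, and the role of Registry 3 is unstated.

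**Section 11.0 does not promise sensitivity or specificity at the cut-off, nor say that a best IPMS measure will be picked.** Both true. The point is therefore conditional: it applies to whatever accuracy is reported at the cut-off, and the multiple-measure figures apply only if a selection is made.

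**An unadjusted ROC is legitimate for prediction.** This stands. A reader might infer that the plan claims an independent or causal IPMS effect that the ROC cannot support, since LV size could drive both IPMS and recurrence. The documents do not go that far. Sections 2.0, 3.0 and 11.0 speak of prediction, stratification and correlation. The hypothesis says risk factor without calling it independent. The effect of reducing IPMS is a secondary objective, for which section 11.0 provides only a pilot, and mechanism is left to modelling. The phrase "independent of the left ventricular size or volume" in section 3.0 describes an earlier study of regurgitation at presentation, not a planned analysis of recurrence. What remains is a caution about how the ROC result is worded.

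**Conclusion.** The point holds, and should be dealt with before analysis. As written, accuracy reported at the chosen cut-off would on average be optimistic by about 0.08–0.10 in Youden's index at n = 125, by 0.14–0.16 if the cut-off were fixed on phase 1, and by about 0.04 at n = 500. The cut-off itself is poorly determined. These sizes rest on 32.6% recurrence, binormal IPMS, the Youden rule and true AUC 0.65–0.75. The direction follows from choosing and scoring a cut-off in the same data, and it is an average, not a certainty for one data set.

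The overlap at 2+ depends on no assumption; it is an error in the stated rule.

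Two stronger readings are not supported. The AUC of a single pre-specified measure is not inflated. Nor can lack of adjustment be called a flaw in a predictive cut-off. Adjusting for one covariate would not license an independent or causal reading either. Suppose IPMS has no effect of its own, n = 125, and LV size is the only confounder (assumed IPMS–LV correlation 0.5–0.7, LV AUC 0.65–0.75). The adjusted test is then falsely significant in about 4–7% of studies when LV size is measured perfectly, but in as many as 12% at reliability 0.8 and 23% at 0.7.

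**What to change.** 1. Make the section 11.0 outcome exclusive by assigning grade 2+ to one class; which class is for the clinical team to decide.
2. Keep the ROC. Name one primary IPMS measure (phase and level) and the cut-off criterion, and state whether Registry 3 patients enter. Report bootstrap optimism-corrected sensitivity and specificity, with a confidence interval for the cut-off. If measures are selected, repeat the selection inside the bootstrap and correct the AUC too.
3. Limit the ROC conclusion to prediction. Optionally add a logistic model of 12-month recurrence on continuous IPMS, adjusted for pre-operative LV end-systolic volume index (already collected under section 9.0), as a supportive odds ratio with interval. State that it does not establish an independent or causal effect, because other confounding and measurement error in LV size remain.
4. In section 3.0, call the same-patient force modelling mechanistic support, not validation of the cut-off.

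**Cost.** SAP wording and modest computation, with no new data. Reported accuracy will look slightly less favourable, and about one-third of the optimism will remain after the bootstrap. With 41–45 events the adjusted estimate is imprecise: at an assumed IPMS–LV correlation of 0.5, an odds ratio of 1.5 per SD has a typical 95% interval of 0.93–2.42, and one of 2.0 has 1.19–3.36. It should be read as an estimate, not a pass/fail test.

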## 1.0 PROTOCOL SUMMARY

Title	Improving mitral repair for functional mitral regurgitation (IMPROVE-FMR)
Precis	
Functional mitral regurgitation (FMR) can have an adverse impact on the cardiomyopathic left ventricle, by imposing a chronic low-pressure volume overload. Unrepaired FMR increases the risk of congestive heart failure and death. Undersizing mitral annuloplasty (UMA) is the current gold standard for repair of FMR, but its outcomes are poor with 32.6% of patients presenting with clinically significant recurrent FMR at 1 year after the repair, which increases to 58.8% of the patients at 2 years after annuloplasty. Currently, we do not understand why some patients have failure of annuloplasty, while others do not. Lack of mechanistic insights has inhibited an evidence driven approach in optimizing the repairs adequately – resulting in plethora of new sub-valvular techniques, but very few with appropriate scientific justification to be tested in randomized trials.
 
Our team recently performed a retrospective cardiac MRI study in FMR patients and identified that inter-papillary muscle separation (IPMS) is a strong determinant of FMR severity prior to undergoing any repair. Using image-derived computational biomechanical modeling, we reported that when IPMS is elevated, marginal chordal forces restrict parallelization of the leaflet edges and cause higher FMR. We built upon this observation, and performed an ex vivo bench study to demonstrate that IPMS is a strong determinant of repair success as well. In this study, we demonstrated that the MR volume after repair is directly correlated to the pre-operative IPMS. We recently advanced this study further into a chronic swine model, and demonstrated that swine undergoing papillary muscle approximation (PMA) alone or concomitantly with undersizing mitral annuloplasty (UMA), have better valvular function at 3 months after surgery, compared to animals that receive UMA alone. Their valvular kinematics were superior, and so was their ventricular function.
 
In this observational, prospective, non-randomized study in humans with FMR, we seek to investigate the following:
 

• Question 1: Does pre-operative IPMS correlate with the severity of FMR after UMA at 30 days, 6 months and 12 months. We will study this primary objective by conducting pre-operative MRI and echo in patients receiving UMA, and follow them to one year. Secondly, we will use these images from each patient as input to a computational biomechanical model, which will help demonstrate the chordal forces and stresses before repair, after repair and at the follow-up time points. We will recruit a total of 125 patients to this phase of the study.

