of FMR after annuloplasty. Since high or low are subjective terms, we seek to recruit 125 patients undergoing undersizing mitral annuloplasty (UMA) at our institution and measure their inter-papillary muscle separation before and after the procedure, and study their impact on 12 month outcomes of the repair. We will perform statistical analysis to determine a cut-off value for IPMS that can stratify patients at risk for UMA failure.

Using the patient specific imaging that we obtain from the 125 patients, we will perform comprehensive biomechanical computational modeling to demonstrate and validate that patients below the cut-off value of IPMS have better mitral valve force distribution, vs. those above the cut-off value of IPMS having poor mitral valve force distribution. This data will help validate the cut-off value as a viable technique to stratify patients for UMA.

In the final step of this study, we will demonstrate that those patients with higher IPMS and at risk of UMA failure, may benefit from a concomitant papillary muscle approximation technique. We will recruit 15 patients to a pilot study, in whom IPMS is above the cut off value, and perform papillary muscle approximation (PMS) along with undersizing mitral annuloplasty (UMA). We will investigate the effect of this combination approach on the outcomes at 6 months and 12 months.

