#### **4.0 CLINICAL AND SCIENTIFIC JUSTIFICATION**

Failure of undersizing mitral annuloplasty (UMA) in patients with FMR is now an established fact. High rates of FMR recurrence after UMA have been reported in several studies, but a mechanistic basis for such failure is lacking. Due to the high rates of repair failure, these patients are receiving a mitral valve replacement (MVR), which is known to have poor durability and higher mortality. Thus, the clinical justification to understand the mechanisms underlying UMA failure is solid. The knowledge gained from this study may not directly impact these patients, but is expected to improve the treatment options available to other patients in the future.

The scientific justification for studying inter-papillary muscle separation (IPMS) as a determinant of UMA failure, stems from our previous published study. In 2014, we reported that elevated IPMS correlated with higher severity of FMR in humans. In a subsequent study in a bench model, we reported that elevated IPMS has a direct impact on valve function after UMA. Based on these two studies, we developed the hypothesis that a cut-off value for IPMS exists, which can determine who patients could have a durable repair with UMA, and which patients may require additional procedures. Based on this information, for those with higher IPMS we are proposing that papillary muscle approximation (PMA) may be a useful technique to reduce their IPMS and improve their suitability for UMA.

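### The plan asks whether an IPMS cut-off can be established but does not tie the ROC-derived cut-off to any evidence that IPMS predicts recurrence

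*Combined protocol and SAP*

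**What the plan says.** Section 2.0 (Objective) first asks whether IPMS predicts FMR severity at 12 months after UMA, and then "whether a cut-off value of pre-operative inter-papillary muscle separation can be established to predict patients who might have failure of UMA". Section 4.0 states the matter as a hypothesis: "we developed the hypothesis that a cut-off value for IPMS exists". Section 3.0 (Background) takes the existence of a cut-off as given: "We will perform statistical analysis to determine a cut-off value for IPMS that can stratify patients at risk for UMA failure".

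The only method is in section 11.0 (Analysis Plan): "An ROC curve analysis will be used to determine the inflection point of inter-papillary muscle separation at which FMR will recur at 12 months". The predictor is described there as follows: "Pre-operative inter-papillary muscle separation will be measured and is a continuous variable". The outcome is recurrence, yes or no.

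Section 11.0 also states a correlation objective (IPMS against post-operative FMR grade), and the primary endpoint in sections 1.0 and 9.0 is that correlation. No test, alpha or decision rule is given for it, and the cut-off is not made to depend on it. The documents give no minimum AUC, no confidence interval or test against 0.5, no minimum sensitivity or specificity, and no result that counts as no cut-off.

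Section 3.0 then uses the cut-off twice: to form the groups for the force-distribution comparison, and to select the 15 patients for the pilot of added papillary muscle approximation (PMA).

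**The concern.** The objective is a yes/no question, but the analysis only returns a number. An ROC curve built from pure noise still has a best point, so the existence of that point cannot separate a predictive IPMS from an unrelated one. If the number is carried forward without a check, a noise-derived value could define the biomechanical comparison and the pilot population, and could be reported as a way of stratifying UMA patients. The validation described in section 3.0 does not supply the check: it is computational modelling in the same 125 patients and has no failure criterion.

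**Working it through.** **Inputs from the documents**
- UMA group (section 1.0, Sample size): "125 patients to receive UMA and followed to 12 months, with interim imaging".
- 12-month recurrence, first figure (section 1.0, Precis): "32.6% of patients presenting with clinically significant recurrent FMR at 1 year after the repair". 125 × 0.326 = 40.75, about 41 events and 84 non-events.
- 12-month recurrence, second figure (section 3.0): "At 12 months, ~36% of the patients present with recurrence FMR". 125 × 0.36 = 45 events and 80 non-events.
- Phase 1 (section 11.0): 50 UMA patients.
- IPMS measures: three phase measures (section 9.0, primary endpoint) × three locations (section 9.0, IPMS definition) = up to nine.

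The 125 cannot be reproduced, because the documents give no alpha, power, effect size or target AUC.

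**Assumptions**
- The ROC point is the maximum of J = sensitivity + specificity − 1 (Youden), with higher IPMS predicting recurrence. A closest-to-corner rule always returns a point, so the conclusion does not depend on this choice.
- For power: binormal IPMS with equal variances and true AUCs of 0.60 to 0.75. The documents give no AUC.

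**Step 1. How often does a null dataset give a cut-off with J > 0?**
With no association, all orderings of events and non-events are equally likely. When the two counts share no common factor and there are no ties, P(max J > 0) = 1 − 1/N. For 41 and 84: 1 − 1/125 = 0.992. For 45 and 80, which share a factor of 5, a direct path count gives 0.9919.

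| Setting | P(max J > 0), no association |
|---|---|
| N = 125, 32.6% or 36% recurrence | 99.2% |
| N = 100 | 99.0% |
| N = 50 | 98.0% |
| N = 125, IPMS rounded to 1 mm (assumed SD 6 mm) | 98.5% |
| N = 125, best of 3 or 9 measures | about 100% |

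Simulation agrees (99.2% and 99.1% at N = 125). Section 11.0 places MR of exactly 2+ in both outcome categories, so the event count is not fully defined. This hardly moves the result.

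**Step 2. What does the null cut-off look like?**
At N = 125 the median best J is about 0.10 and its 95th percentile about 0.22. The share of patients above the cut-off runs from about 2% to 98% (central 95%).

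**Step 3. A gate on the AUC**
Declare a cut-off only if AUC − 1.96 × SE > 0.5 (DeLong SE).

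| True AUC (assumed) | N = 125, 32.6% recurrence | N = 50 |
|---|---|---|
| 0.50 | 2–3% | 2–3% |
| 0.60 | about 46% | about 20–23% |
| 0.65 | about 80% | about 44% |
| 0.70 | about 96% | about 66% |
| 0.75 | about 99.7% | about 87% |

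**Step 4. Multiplicity**
The 2–3% holds for one pre-specified measure. At N = 125, with an assumed correlation of 0.7 between measures, the same gate applied to the best of 3 passes in about 6% of null studies, and to the best of 9 in about 11%.

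**The case against.** **Locating a point is not declaring success.** Section 11.0 names no Youden rule and nowhere says that finding a point means that a cut-off has been established. A reader might infer from the 99% that the study has a false-positive rate near 100%, or that the question can never be answered no. The documents do not support either. The 99% is close to a mathematical identity that holds for any ROC analysis of unrelated data. A null index of about 0.10 is visibly weak, and the investigators could decline to act on it. What stands is that such a refusal would be a post hoc judgement: the plan gives no criterion for it.

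**The primary analysis can be null.** A reader might also infer that the plan confirms its hypothesis whatever the data. It does not. The hypothesis in section 1.0 is that elevated IPMS is a risk factor for recurrence, and the primary correlation could show no relation. The gap is narrower: a null correlation and a reported cut-off could stand side by side, because nothing connects them.

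**An AUC gate tests association, not a threshold.** This is correct. The simulated data in step 3 contain no true threshold, yet the gate passes in about 96% of studies at AUC 0.70. Passing it justifies reporting a cut-off. It does not prove that a biological threshold exists.

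**This is a single-center observational study with an unpowered pilot.** That limits the consequences, but section 2.0 puts the cut-off question within the primary objective and section 3.0 puts the answer to use.

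**Conclusion.** The point holds in this limited form: the plan does not make the cut-off depend on evidence that IPMS predicts recurrence, so producing a cut-off is not evidence that one has been established. Under the assumed Youden criterion, about 99% of null datasets of 125 patients give a cut-off with a positive index. The figure stays between 98% and 100% across the recurrence rates, sample sizes and rounding examined. The size of the resulting error depends on how the investigators would treat a weak cut-off, which the documents do not say, so no false-positive rate for the study's conclusion can be given. The change is worth making because the number feeds two later steps and the remedy needs no new data. The gate's pass rates rest on the binormal model and the assumed AUCs.

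**What to change.** In section 11.0:
1. Name one pre-operative IPMS measure (phase and location) in advance, or state a multiplicity adjustment across the up to nine available.
2. Report its AUC for 12-month recurrence in UMA patients with a two-sided 95% CI (DeLong or bootstrap).
3. Describe a cut-off as established only if the lower limit exceeds 0.5 in the hypothesised direction (higher IPMS, more recurrence). Otherwise report the AUC and CI and state that no cut-off was established.
4. Describe a passing result as evidence of association sufficient to report a cut-off, not as proof that a threshold exists.

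Refer to this rule in section 2.0 as the answer to the cut-off question.

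The text costs a few sentences. The real cost is that the study may have to report no cut-off: at N = 125 and a true AUC of 0.60 this happens in about 100 − 46 = 54% of studies, and at 0.70 in about 100 − 96 = 4%. Section 11.0 places the PMA pilot in phase 2, after 50 UMA patients, whereas section 3.0 can be read as deriving the cut-off from all 125. If the gate were applied after phase 1, the chance of no cut-off would be about 100 − 66 = 34% even at a true AUC of 0.70. Sections 3.0 and 11.0 must therefore be reconciled on when the cut-off is derived, and section 3.0's use of it for pilot selection must be reconciled with the possibility that none is established.
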